**4.1 Screening Period (Visit #1)**

Visit #1 will include the following procedures to be performed:

- | [REDACTED]
- | [REDACTED]
- | [REDACTED]
- | [REDACTED]
- | [REDACTED]
- | [REDACTED]
- | [REDACTED]
- | [REDACTED]
- | [REDACTED]
- | [REDACTED]
- | [REDACTED]
- | [REDACTED]
- | [REDACTED]
- | [REDACTED]
- | [REDACTED]
- | [REDACTED]
- | [REDACTED]
- | [REDACTED]
- | [REDACTED]
- | [REDACTED]
- | [REDACTED]

**4.2 Randomisation/Baseline/Treatment Visit (Visit #2)**

Baseline/Treatment (Day 0) Visit #2 [REDACTED] [REDACTED] y. Before randomisation, the investigator or the study nurse will call the patient to confirm his/her participation to the study. Promptly after patient participation confirmed, the patient will be given a unique Randomisation Number and will be allocated to one of the four study arms (JTA-004 50 2ml or 4 ml, JTA-004 100 2 ml, or Reference) through IWRS platform.

**JTA-KOA1 - Clinical Study Protocol**

JTA-KOA1-CSP

V 04

Author: EB

Date: May 10, 2017

Pg. 46/114

During Visit #2, the following procedures will be performed:

- | [REDACTED]
- | [REDACTED]
- | [REDACTED]
- | [REDACTED]
- | [REDACTED]
- | [REDACTED]
- | [REDACTED]
- | [REDACTED]
- | [REDACTED]
- | [REDACTED]
- | [REDACTED]
- | [REDACTED]
- | [REDACTED]
- | [REDACTED]
- | [REDACTED]

During the whole study follow-up after IA of JTA or reference product, patients must not receive any IA treatment in the target knee (either hyaluronic acid or corticoids injection). If such IA injection is performed, reasons must be documented in the concomitant medications section and the patient must be withdrawn from study. The “Early Termination Form” must be completed in such case.

#### 4.3 Follow-up Visit #3 (Week 2 [REDACTED])

During this visit, the following procedures will be performed:

- | [REDACTED]
- | [REDACTED]
- | [REDACTED]
- | [REDACTED]

**JTA-KOA1 - Clinical Study Protocol**

JTA-KOA1-CSP

V 04

Author: EB

Date: May 10, 2017

Pg. 48/114

## 5 RATIONALE FOR THE STUDY DESIGN

### 5.1 Study Rationale

Bone Therapeutics S.A. has developed an enhanced HA-based viscosupplement (JTA-004) with stabilising effects on the joint mechanical integrity. Compared to other HA-based preparations, the novelty of JTA-004 lies in its composition and formulation expected to extend its action, as JTA-004 includes active substances with gelification properties and analgic and anti-inflammatory properties. Single injection of JTA-004 is therefore intended to provide prolonged relief of OA symptoms.

The overall goal of JTA-KOA1 is to determine JTA-004 safety, select the best strength in terms of efficacy and compare it to an approved viscosupplement.

### 5.2 Types of Osteoarthritis

Knee OA is classified in four severity grades, from doubtful to severe, according to the Kellgren-Lawrence grading system. This categorical scale incorporates important radiographic features of OA (see Annex 5).

In order to have a study population as homogenous as possible and to avoid patients with doubtful and severe OA, the study will only include patients with Grade II and Grade III symptomatic knee OA.

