### 3.4.3 Radiological Evaluation

The Principal Investigator or the radiologist must grade the severity of OA according to Kellgren-Lawrence Radiographic Score. For the purpose of this study, radiographic assessment is only required on the target knee [REDACTED]

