## JTA- KOA1 - Clinical Study Protocol

JTA-KOA1-CSP	V 04	Author: EB	Date: May 10, 2017	Pg. 40/114
--------------	------	------------	--------------------	------------

- Ambulatory (able to walk unassisted, the use of a crutch or a walking stick is allowed)
- Diagnosed with primary knee OA, fulfilling the following American College of Rheumatology (ACR) criteria at the target knee:
  - Pain  $\geq$  40 mm on a 0-100 mm VAS during the 3 days preceding the date of the Screening Visit (see Annex 2)
  - Morning stiffness not exceeding 30 minutes
  - Kellgren-Lawrence grade II or III (confirmed by X-ray within the last 6 months)
- Insufficient/failed response to analgesics and/or NSAID
- Willing and able to abstain from physical therapy of the knee and knee braces for the entire duration of study
- Capable to understand and comply with study requirements and to provide a written, dated, and signed informed consent prior to any study procedure for participation in the study and transmission of personal "anonymized" data

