#### 10.7.5 Primary Endpoint

The mean change in the WOMAC® VA3.1 pain subscale score of JTA-004-treated patients between baseline and Month 6 will be compared to the mean change in the WOMAC® VA3.1 pain subscale score of the reference-treated patients between baseline and Month 6.

The following hypothesis is stated to show superiority of JTA-004 to Reference:

H0: The difference in the mean change from baseline at Month 6 between JTA-004 and Reference is superior or equal to 0.

H1: The difference in the mean change from baseline at Month 6 between JTA-004 and Reference is inferior to 0.

This hypothesis is expressed mathematically by:

H0: MeanJTA-004 - MeanReference ≥ 0 versus

H1: MeanJTA-004 - MeanReference < 0

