#### 10.7.6 Secondary ██████████ Endpoints

For the analysis of the secondary endpoints,

- WOMAC® VA3.1 pain subscale (WOMAC® subscale A) at Month 3
- WOMAC® VA3.1 total score over time

groups will be compared using a parametric or non-parametric ANCOVA (according to the normality of data and the homogeneity of the variances) with the following factors: baseline value and group. Repeated measures analyses will be performed on longitudinal data.

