### 10.8 Randomisation

Patients will be randomised in one of the three JTA-004 groups or in the reference group according to a 1:1:1:1 ratio using IWRS.

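### The one readable ANCOVA (10.7.6, secondary endpoints) leaves out Kellgren-Lawrence grade, a baseline factor known for every eligible patient: a small missed gain in precision

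*Combined protocol and SAP*

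**What the plan says.** Section 5.2 (Types of Osteoarthritis) opens its restriction with "In order to have a study population as homogenous as possible and to avoid patients with doubtful and severe OA" and concludes that "the study will only include patients with Grade II and Grade III symptomatic knee OA". Section 3.5.2 makes this an entry criterion: "Kellgren-Lawrence grade II or III (confirmed by X-ray within the last 6 months". Grading is mandatory under 3.4.3: "The Principal Investigator or the radiologist must grade the severity of OA according to Kellgren-Lawrence Radiographic Score". Section 3.5.1 places the check of eligibility in a screening period that precedes randomisation.

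On analysis, 10.7.6 opens with "For the analysis of the secondary endpoints", lists WOMAC pain at Month 3 and WOMAC total score over time, and specifies a parametric or non-parametric ANCOVA "with the following factors: baseline value and group". Section 10.7.5 gives the hypotheses for the primary endpoint, the alternative being "The difference in the mean change from baseline at Month 6 between JTA-004 and Reference is inferior to 0", and names no model or covariate in the text that can be read.

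On allocation, 10.8 says only "Patients will be randomised in one of the three JTA-004 groups or in the reference group according to a 1:1:1:1 ratio using IWRS". Part of the corresponding sentence in 3.3.2 is blacked out.

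**The concern.** The protocol singles out radiographic grade as something worth controlling through entry, yet two grades remain in the trial. Table 9 labels them minimal and moderate. Grade is a radiographic measure and is distinct from the baseline score already in the model. If grade II and grade III patients change by different amounts, that difference stays in the residual variance of the 10.7.6 comparisons. In any one trial, a chance difference in grade mix between two arms also moves the estimated treatment difference. A prespecified term would remove both effects using a value the trial already collects.

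At stake are a little precision and the freedom to adjust without challenge: a covariate added after an imbalance has been seen is much harder to defend than one named beforehand.

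**Working it through.** **Inputs from the plan (10.9).** Difference 7 mm, SD 10.5 mm, two-sided 5%, 80% power, 37 evaluable per group, 41 per group with dropout. These belong to the Month 6 primary comparison. They illustrate size only, because no planning figures are readable for the secondary endpoints.

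**Assumptions, not in the documents.** Half the patients are in each grade. Mean change differs between grades by d = 2 to 7 mm. The 10.5 mm SD is the SD before adjustment for grade.

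**Step 1: reproduce the plan's figure.** A two-sample t-test with 7/10.5 = 0.667 needs 36.3 per group, so 37, as stated. Power at 37 per group is 80.8%. The standard error of the difference is 10.5 × √(2/37) = 2.44 mm.

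**Step 2: gain from adding grade.** With a 50/50 split, R² = 0.25 × d² / 10.5². The residual SD is 10.5 × √(1 − R²), and power is recomputed at 37 per group.

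| d (mm, assumed) | R² | Residual SD (mm) | Power | n per group for 80% |
|---|---|---|---|---|
| 0 | 0 | 10.50 | 80.8% | 37 |
| 2 | 0.9% | 10.45 | 81.1% | 36 |
| 3 | 2.0% | 10.39 | 81.5% | 36 |
| 5 | 5.7% | 10.20 | 83.0% | 35 |
| 7 | 11.1% | 9.90 | 85.1% | 33 |

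The gain runs from 0.3 to 4.3 percentage points of power, or 1 to 4 fewer patients per group for the same 80%.

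**Step 3: chance imbalance.** With 41 per arm and half in grade III, the SD of the between-arm difference in grade III share is √(2 × 0.25/41) = 0.110, or 11 percentage points. A gap of at least 15 points needs a difference of 7 patients (6/41 = 14.6%, 7/41 = 17.1%). Its exact binomial probability for one given pair of arms is 15.1%.

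**Step 4: what a 15-point gap does.** The shift is 0.15 × d: 0.15 × 2 = 0.30 mm up to 0.15 × 7 = 1.05 mm, against the planned 7 mm.

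**Step 5: is that shift extra to the standard error?** No. The variance of the unadjusted difference is 10.5² × 2/37 = 5.96, whose square root is the 2.44 mm above. At d = 7 the part due to chance differences in grade mix is 49 × 0.25 × 2/37 = 0.66, and 0.66/5.96 = 11.1%, which is the R² in the table. The imbalance is a component of the stated standard error and is not added to it.

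**The case against.** The strongest reply is that nothing here is wrong. Under randomisation a comparison that ignores grade is unbiased and keeps its type I error, and Step 5 shows that chance imbalance is already inside the standard error. This stands.

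A second reply is that 5.2 explains why doubtful and severe disease is excluded; the restriction is itself the control of heterogeneity, and the section does not say that grades II and III respond differently. This also stands, so the size of any gain rests on assumption. At 2 to 3 mm between grades, power reaches only about 81.5%.

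Third, a reader might infer that the Month 6 primary analysis omits grade. The documents do not support that. The two-term model is stated for the secondary endpoints, 10.7.5 shows no model, and parts of section 10 are missing from the public text or blacked out. The selection of the best strength uses Month 3 pain, but its model is not readable either.

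Fourth, a reader might infer that allocation is stratified by grade and the model ignores it, or that it is unstratified and imbalance goes unaddressed. The redaction in 3.3.2 falls where a stratification factor could be named, so neither can be established.

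A larger effect is also tempting. A 10 mm difference between grades would imply R² = 0.25 × 100/110.25 = 22.7%. That difference would exceed the planned drug effect and equal the 10 mm that the protocol cites as the minimal clinically important difference. Nothing in the documents supports it.

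What survives is narrower: the 10.7.6 model is explicit, grade is collected before randomisation, and it is not used.

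**Conclusion.** The point holds as an inexpensive improvement to the secondary-endpoint ANCOVA in 10.7.6. It does not establish a defect in the primary analysis. Leaving grade out costs a little precision, introduces no bias, and invalidates no figure in the plan.

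On the assumed 2 to 7 mm difference between grades and an even split, the gain is about 0.3 to 4.3 percentage points of power on the Month 6 planning figures. A 15-point imbalance, with a probability of about 15% for a given pair of arms, would move the estimate by 0.3 to 1.05 mm, within a standard error of 2.44 mm. If the grades do not differ in pain change, the gain is nil.

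**What to change.** In 10.7.6, prespecify Kellgren-Lawrence grade (II/III) as a fixed factor beside baseline value and group, or give a reason for leaving it out. Use the same term in the Month 6 model if it is not already there. Include in both models any factor on which the IWRS stratifies, since omitting one tends to make standard errors too wide. Fix this before any unblinding, including the interim analysis.

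The cost is one degree of freedom for grade and no new data. Because 10.7.6 allows a non-parametric ANCOVA, the text must also say how that version carries the extra factor; it is not simply one more term there.

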### 5.3 Clinical and Biological Evaluation Tools

#### 5.3.1 *Clinical Evaluation*

The usual tool to assess pain is the VAS. This tool allows reliable assessment of symptoms (Breivick *et al.*, 2008). A VAS is a measurement instrument dedicated to the evaluation of characteristics, attitudes or symptoms that is believed to range across a continuum of values and cannot easily be directly measured (e.g., pain or general health status in this particular study). In VAS, the symptom that a patient feels ranges across a continuum from no symptom

---

 Human plasma and the alpha-2 adrenergic receptor agonist 2,6-Dichloro-N-2-imidazolidinylidenebenzenamine hydrochloride

## JTA-KOA1 - Clinical Study Protocol

JTA-KOA1-CSP

V 04

Author: EB

Date: May 10, 2017

Pg. 49/114

(0 mm) to extreme symptom (100 mm) on a horizontal line of 100 mm in length. The patient marks on the line the point that he/she feels, represents his/her perception of his/her current status of symptom. The VAS score is determined by measuring in millimetres from the left hand end of the line to the point that the patient marks (see Annex 2).

### WOMAC®

Clinical evaluation of the knee is usually performed using dedicated open questionnaires and/or scores, which have been developed and established in order to assess knee pain, knee stiffness, and/or knee function (physical disability) in patients with primary OA, but also for other knee diseases. These include the Lequesne and WOMAC® Scores.

Patients will be assessed using the WOMAC® Index. The WOMAC® Osteoarthritis Index is a tri-dimensional, self-administered, patient-centred health status questionnaire for knee disease severity and osteonecrosis symptoms (see Annex 1).

Although the Lequesne score is frequently used and cited in the literature, it presents a number of limitations and pitfalls regarding its use in clinical practice. Indeed, it has demonstrated its usefulness and efficacy as an outcome functional measure after hip surgery only (Lequesne *et al.*, 2003; Stucki *et al.*, 1998). By contrast, the WOMAC® Index, which allows a thorough evaluation of pain, stiffness, and function (through 3 subscales with a total of 24 questions), has been widely validated and used: it has been standardised and tested for reliability, validity, and responsiveness in patients with knee OA in various clinical settings, including both medical (pharmacological) and surgical management (total hip replacement) of patients (Bellamy, 2002; Bellamy, 2005; Bellamy *et al.*, 1988).

Moreover, and contrarily to the other knee scores, the WOMAC® Index is available not only in Likert scale format but also in VAS format. Indeed, VAS has been suggested to be more reproducible and sensitive compared to Likert scales (Gerich *et al.*, 2007).

As for primary endpoint, the WOMAC® Index pain subscale will be used.

However, the WOMAC® Index total score, stiffness and function subscales will be used as secondary endpoints.

The minimal clinically important difference (MCID) represent the smallest difference in score in the domain of interest which patients perceive as beneficial and which would mandate, in the absence of troublesome side effects and excessive cost, a change in the patient's management

**JTA-KOA1 - Clinical Study Protocol**

JTA-KOA1-CSP	V 04	Author: EB	Date: May 10, 2017	Pg. 50/114
--------------	------	------------	--------------------	------------

(Beaton *et al.*, 2002). For the WOMAC® Index pain subscale, the MCID, expressed in a percentage of the baseline is defined in the literature as a difference of 20% or 10 mm of the baseline (Ehrich *et al.*, 2000; Bellamy *et al.*, 2005).

[Redacted text block containing multiple lines of blacked-out content]

**JTA-KOA1 - Clinical Study Protocol**

JTA-KOA1-CSP

V 04

Author: EB

Date: May 10, 2017

Pg. 51/114

#### 5.4 Rationale for Choice of Reference Group

Active comparators should be chosen with care. An example of a suitable active comparator would be a widely used therapy whose efficacy in the relevant indication has been clearly established and quantified in well designed and well documented superiority trial(s) and which can be reliably expected to exhibit similar efficacy in the contemplated active control trial (ICH E9). Optimally, this is demonstrated by finding that the active treatment intended for use as the active control was reliably found superior to placebo.

For these reasons, among the several commercially available HA preparations, Synvisc-one® was selected as reference in this clinical trial. Indeed, Synvisc-One® is an approved and well-established treatment of knee OA in Europe and USA. Three clinical trials have shown that Synvisc-One® is safe and effective by providing statistically significant and clinically relevant pain relief in patients suffering from knee OA. The first study (Conrozier et al., 2009) demonstrated that a single 6 ml intra-articular injection of Synvisc-One® is as safe and effective that multiple injection (2 ml, three time, one week apart) in providing statically significant, clinically relevant pain relief, as measured by WOMAC® A pain scores at 24 weeks. A change from baseline at 24 weeks of -34.9 mm (corresponding to a mean percentage change in pain from baseline of 54.7 %). The second study (Chevalier et al., 2010), a controlled randomised, multicenter, double-blind study, compares a single (6 ml) IA injection of Synvisc-One® to a placebo (PBS). This study demonstrated that a single 6 ml intra-articular injection of Synvisc-One® provides statically significant, clinically relevant pain relief, as measured by WOMAC® A pain scores over 26 weeks, with a modest difference compared with placebo (-3,0 mm, SEM 1,52, p = 0.047). An estimated change from baseline over 26 weeks of -21 mm (corresponding to a mean percentage change in pain from baseline of 36 %) is observed for Synvisc-One® versus an estimated change from baseline of -17,25 mm (corresponding to a mean percentage change in pain from baseline of 29 %) observed for placebo demonstrating that Synvisc-One® is reliably superior to placebo. The last study (Drieser et al., 2015) compared a high molecular weight hyaluronan (Ostenil®Plus) to Synvisc-One®. In this randomised, double-blind study, an estimated change from baseline after 26 weeks of -34.3 mm (corresponding to a mean percentage change in pain from baseline of 58.9 %) is observed for Ostenil®Plus versus an estimated change from baseline of -36.2 mm (corresponding to a mean percentage change in pain from baseline of 62.5 %) observed for Synvisc-One® demonstrating that both treatments provide statistically significant and clinically relevant pain relief.

## 6 INVESTIGATIONAL MEDICINAL PRODUCT AND REFERENCE TREATMENT

### 6.1 Treatments Administered

#### 6.1.1 Investigational Medicinal Products

The investigational medicinal products (3 different strengths: JTA-004 50 (2ml), JTA-004 50 (4ml) and JTA-004 100 (2ml)) will be provided [REDACTED]

[REDACTED]

[REDACTED]

[REDACTED]

[REDACTED]

[REDACTED]

[REDACTED]

[REDACTED]

[REDACTED]

[REDACTED]

#### 6.1.2 Reference

The reference treatment, Synvisc-One®, is a sterile viscoelastic solution provided in a ready-to-use syringe. The six millilitre solution contains 48 mg sodium hyaluronate.

### 6.2 Treatment with Investigational medicinal products and reference

#### 6.2.1 Reconstitution Procedure

[REDACTED]

[REDACTED] The reference product is provided in a ready-to-use syringe and does not need reconstitution.

#### 6.2.2 Injection Procedure

[REDACTED]

[REDACTED]

JTA-KOA1 - Clinical Study Protocol

JTA-KOA1-CSP

V 04

Author: EB

Date: May 10, 2017

Pg. 53/114

[REDACTED]

[REDACTED]. The injection is accomplished following puncture through the skin and into the joint space. If resistance is encountered, redirection of the needle may be necessary. The use of local anaesthesia with lidocaine prior to the IA injection is at the discretion of the Independent Physician.

The injections will be performed by an Independent Physician who are very well experienced with this type of administration to limit the risk of periarticular administration. Products should be injected in the synovial space only and not into blood vessels, extra-articularly, or in the synovial tissue or capsule. If the whole volume of Investigation Medicinal Product cannot be injected, the reason must be documented in the eCRF.

The products are intended for single use and strict aseptic administration technique must be followed. For the reference, the syringe containing the HA solution should be used immediately [REDACTED] in order to guaranteed the sterility of the product.

If effusion is found in the knee upon needle placement in the joint space, it must be removed before lidocaine and JTA-004 or reference product is injected. [REDACTED]

[REDACTED]

The administration procedure is summarised in the Table 2 below:

## JTA-KOA1 - Clinical Study Protocol

JTA-KOA1-CSP	V 04	Author: EB	Date: May 10, 2017	Pg. 54/114
--------------	------	------------	--------------------	------------

**Table 2: Administration of the Investigational medicinal product**

	JTA-004	Reference
Product	JTA-004 50 & 100	Synvisc-One®
Route of administration	(Percutaneous) intra-articular administration	(Percutaneous) intra-articular administration
Single dose	2 or 4 ml	6 ml
Dosage schedule	One single dose per patient on Study Day 0 (Visit #2)	One single dose per patient on Study Day 0 (Visit #2)

### 6.2.3 Post-injection Procedures

After withdrawing the needle from the joint space, light pressure should be applied to the injection site, followed by application of a simple adhesive bandage. The patient will be asked to remain at the Investigation Site for 45 minutes post-injection under clinical and blood pressure monitoring. During this period, the blood pressure is monitored [REDACTED] after intra-articular injection. The blood pressure will be performed when the patient is sitting and one minute after standing up to control for hypotensive effect during the acute phase following the injection. The patient will leave the hospital if no clinical signs of hypotension are present.

The patient should be encouraged to rest the injected joint for 24 to 48 hours. Patients will be advised to wait the next day before returning to normal activities, drive a car or manage a machine. Typically there could be pain associated with the procedure. For post-administration pain management, it is recommended that patients rest and ice the injection site.

All AEs and clinical findings prior, during, and post-injection must be recorded. Patients experiencing pain and swelling at the target joint or any other AE will be instructed to contact the study staff.

